## **7 DATA COLLECTION AND MONITORING**

### **7.1 Data Management and Record Keeping**

The data will be collected and reported on paper case report forms and/or in electronic medical record. Each site will be responsible for data entry into system. In the event of discrepant data, research personnel at each site will resolve items. KPSC will be responsible for the data management of this study, including quality checking of the data by conducting an internal audit review.

### **7.2 Data Monitoring Plan**

Remote and on-site monitoring visits will be conducted at each site in accordance with the study monitoring plan that includes at a minimum, a review of signed ICFs, review of subject eligibility, AE reporting and data integrity. Visits will occur approximately during the screening period, after start of study treatment, and at the end of study.

Monitoring visits will be performed by a Kaiser Permanente employee approved by the Department of Research & Evaluation. In addition, this employee will have been trained and met criteria under applicable KPSC Clinical Trials Standard Operating Procedures.

During the monitoring visits, any finding that pose as an actual or potential risk to the health, safety, welfare, or privacy of a research participant or the integrity of the study may be disclosed to the KPSC IRB by the monitor.

Investigators will permit national and local health authorities, KPSC IRB, KPSC Research & Evaluation, U.S. FDA, Department of Health and Human Services, along with other governmental agencies with responsibilities for the safety of drugs and studies.

### **7.3 Data Safety Monitoring Board (DSMB)**

There will be no Data Safety Monitoring Board (DSMB) for this clinical trial since the study drugs used in this study is FDA approved and is being used in accordance to the approved indication. Additionally, all study procedures are considered standard of care.

### **7.4 Retention of Study Record**

Records and documents pertaining to the conduct of this study, including Informed Consent Forms, case report forms, Patient Reported Outcome data, drug accountability logs, IRB submissions, approvals and correspondence, and any regulatory documents, must be retained by the Sponsor-Investigator for at least 15 years after completion or discontinuation of the study, or for the length of time required by relevant Federal or local regulations, whichever is longer. After this time period, study documents may be destroyed per local regulations after receipt of written approval by the Sponsor-Investigator and KPSC Research & Evaluation. Written notification must be provided to the Sponsor-Investigator and KPSC Research & Evaluation prior to moving records to another location or when transferring any records to another party.

## **8 STATISTICAL CONSIDERATIONS**

This is an open label, non-randomized, study with one study arm. Descriptive statistics will be used to describe the observed sustained virological response rate and patient adherence to the treatment regimen. The primary analysis, to evaluate SVR12, will occur after all subjects have completed or prematurely discontinued the study.

The intent-to-treat population will consist of all enrolled subjects in this study. The primary efficacy analysis on clinical outcomes will be performed on all subjects in the intent-to-treat population. The modified intent-to-treat population will include all who receive at least one dose of study drug.

No data will be imputed for any efficacy or safety analyses except for analyses of the HCV RNA endpoints.

HCV RNA values will be selected for the SVR4 and SVR12 analysis based on the defined visit windows. The visit window for analysis of SVR4 is post-treatment days 2-56, and the visit window for analysis of SVR12 is post-treatment days 57-168. The latest available value within each window will be used to define the SVR 4 or SVR12 result.

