### **2.2 Secondary Objective**

The secondary objectives of the study are as follows:

- To evaluate sustained virological response rate 4 weeks after completion of treatment (SVR4) with VIEKIRA PAK (ombitasvir, paritaprevir/r, dasabuvir), with or without ribavirin in a large real world setting
- To evaluate patient adherence with VIEKIRA PAK (ombitasvir, paritaprevir/r, dasabuvir), with or without ribavirin in a real world setting

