### **6.2.3 Treatment Period**

Treatment visits should be based on the subject's Baseline Visit date.

If a subject discontinues or withdraws from the study during the treatment period, he/she should be encouraged to complete the End of Treatment (EOT) Procedures ([Section 6.2.3.3](#)) and the Early Termination Visit ([Section 6.2.4.2](#)) within 14 days of the last study treatment dose. In the event that subject is unable to complete the visit(s) but willing to provide survival status, the study site staff should contact the subject within 14 days to collect the information.

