### **6.2.3.3 Week 12 (Visit 6) - End of Treatment (EOT) Procedures**

The following assessments/procedures will be performed in-clinic:

- Pregnancy Test, Serum or Urine
- Obtain labs:
  - HCV RNA
  - CBC with differential
  - Creatinine
  - Liver panel (ALT, Alkaline Phosphatase, Total Bilirubin), AST and Direct Bilirubin
  - Additional labs as determined by the investigator
- Review concomitant medications
- Review for AEs
- Study drug accountability

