#### **6.2.4.1 Post-Treatment (PT) Week 4 (Visit 7)**

The following assessments/procedures will be performed either in-clinic, or remotely by phone with labs collected at the subject's nearest laboratory facility:

- Pregnancy Test, Serum or Urine
- Obtain labs:

- HCV RNA
- CBC with differential
- Creatinine
- Liver panel (ALT, Alkaline Phosphatase, Total Bilirubin), AST and Direct Bilirubin
- Additional labs as determined by the investigator
- Review concomitant medications
- Review for AEs

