#### **6.2.4.2 Post-Treatment (PT) Week 12 (Visit 8) - End of Study/ Early Termination (ET)**

The End of Study Post-Treatment Week 12 visit will be completed at the conclusion of the post-treatment period.

Early Termination Visit should be completed when a subject discontinues or withdraws from the study during either the Treatment or Post-treatment, except when the reason for discontinuation is confirmed virologic failure ([Section 6.3.3](#)).

If a subject discontinues or withdraws from the study during the treatment period, he/she should be encouraged to complete the End of Treatment (EOT) Procedures ([Section 6.2.3.3](#)) and the Early Termination Visit ([Section 6.2.4.2](#)) within 14 days of the last study treatment dose. In the event that subject is unable to complete the visit(s) but willing to provide survival status, the study site staff should contact the subject within 14 days to collect the information.

If a subject discontinues or withdraws from the study during the post-treatment period, he/she should be encouraged to complete the Early Termination Visit ([Section 6.2.4.2](#)) except when the reason for discontinuation is confirmed virologic failure as described in [Section 6.3.3](#). If a subject is unable to complete the Early Termination visit but willing to provide survival status, the study site staff should contact the subject to collect the information.

The following assessments/procedures will be performed in-clinic, or remotely by phone with labs collected at the subject's nearest laboratory facility:

- Pregnancy Test, Serum or Urine
- Obtain labs:
  - HCV RNA
  - CBC with differential
  - Creatinine
  - Liver panel (ALT, Alkaline Phosphatase, Total Bilirubin), AST and Direct Bilirubin
  - Additional labs as determined by the investigator
- Review concomitant medications
- Review for AEs

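### The SVR4 window opens on post-treatment day 2, so an end-of-treatment or Early Termination sample can be scored as response at 4 weeks

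*Combined protocol and SAP*

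**What the plan says.** Section 8 (Statistical Considerations) sets the windows: "The visit window for analysis of SVR4 is post-treatment days 2-56, and the visit window for analysis of SVR12 is post-treatment days 57-168". It then selects the value: "The latest available value within each window will be used to define the SVR 4 or SVR12 result". The Statistical Methods entry of the Protocol Summary gives the same windows and rule. On missing data, Section 8 says: "No data will be imputed for any efficacy or safety analyses except for analyses of the HCV RNA endpoints". It gives no method for that exception.

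The abbreviation list and Section 2.2 define SVR4 as response 4 weeks after treatment is completed. Section 8.3.2 reports it as a simple percentage with a 95% Wilson interval, and Section 8.3 places it in the modified intent-to-treat population.

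Three kinds of visit can supply an HCV RNA value in the SVR4 window:

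- **Post-treatment (PT) Week 4** (6.2.4.1, Appendix A) is timed from the last dose, ±5 days. It may be "performed either in-clinic, or remotely by phone with labs collected" at a nearby laboratory.
- **EOT/Week 12** (6.2.3, 6.2.3.3, Appendix A) is timed from the Baseline Visit, not from the last dose, ±5 days.
- **EOT procedures and the Early Termination visit after early discontinuation** (6.2.3, 6.2.4.2) are due "within 14 days of the last study treatment dose". Section 6.3.1 prefers the day on which study drug is stopped.

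**The concern.** A value from the first two weeks after the last dose shows that virus was suppressed when treatment ended. It does not show that suppression lasted 4 weeks. Because the window opens on day 2, the stated rule cannot tell the two apart when the early value is the only one through day 56. The subjects most exposed are those who leave during treatment, since an Early Termination sample may be their last. The misclassification runs one way: a suppressed early value adds a responder, and an unsuppressed one is a non-response in any case. Section 1.5 names patient dropout as a reason why real-world results with older regimens fell short of trials, so the handling of early leavers is relevant to the study's question.

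**Working it through.** **The plan's own precision figure.** Section 8.3.1 says that with 100 subjects per subgroup the lower 95% limit for SVR12 lies within 7 points of the observed rate. The Wilson interval at 92/100 has lower limit 85.0%, a gap of 7.0 points; at 95/100 it is 88.8%, a gap of 6.2. The figure holds for observed rates of about 92% or more. The plan gives no precision figure for SVR4.

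**When samples can fall (post-treatment days).**

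- PT Week 4: 28 ± 5 = days 23 to 33.
- EOT in a completer: with Week 12 taken as study day 84, the latest visit is 84 + 5 = 89. With the last dose on day 84 this is post-treatment day 5. Other day-counting conventions give day 4 or day 6.
- EOT and Early Termination procedures after early discontinuation: up to day 14.
- SVR12 window: from day 57, so none of these early samples can enter it.

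EOT samples from day 2 to about day 5, and early-discontinuation samples on days 2 to 14, therefore lie inside the SVR4 window. They decide the result only if nothing later is drawn through day 56. A PT Week 4 draw supersedes them. A sample taken on the day of discontinuation falls before day 2 and is outside the window.

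**Does another rule prevent it?** The imputation exception does not: no method is given, and an early sample is an available value, so nothing would be imputed. No other text sets a later minimum day.

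**Size.** One subject is 1/200 = 0.5 point. Table 2 gives adverse-event discontinuation in the non-cirrhotic active arms as 0.5% to 0.8% with ribavirin and 0.4% without. With 100 subjects per arm:

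- lower: 0.5 + 0.4 = 0.9 subjects, 0.9/200 = 0.45 point;
- upper: 0.8 + 0.4 = 1.2 subjects, 1.2/200 = 0.6 point.

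This assumes that every such subject had only a suppressed day 2–14 sample and was not a true week-4 responder, so it is a ceiling for this route.

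**Scale against sampling error (95% true rate assumed).** 190/200 = 95.0%, Wilson 91.0% to 97.3%. With one early-only subject wrongly added, 191/200 = 95.5%, 91.7% to 97.6%. The shift is small beside the width of the interval.

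**The denominator rule matters.** Starting from 191/200 = 95.5%, excluding that one early value gives 190/199 = 95.5% if the subject is dropped, but 190/200 = 95.0% if the subject is kept as a non-responder. Moving the window without stating the denominator would leave the rate almost unchanged.

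**The case against.** The strongest defence is that the windows are contiguous bands around the nominal visits: 56 is midway between days 28 and 84, and 168 = 2 × 84. A ±5-day scheduling tolerance need not be an analysis limit, and the latest-value rule already lets a PT Week 4 draw replace anything earlier. This explains the upper limits but not day 2; the midpoint between the last dose and day 28 would be day 14. It also does not help a subject with no later draw.

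A second objection stands. If every missing SVR4 value were simply counted as failure, a completer who skipped the PT Week 4 draw but was suppressed at PT Week 12 would be an SVR4 failure and an SVR12 success. The fix has to avoid that contradiction.

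Stronger readings are tempting but not supported:

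- **That SVR12 is biased by the early window.** It opens on day 57, beyond any EOT sample or timely Early Termination sample.
- **That SVR4 could shift by several points.** The documents give no total rate of early leaving, and Section 8.3.2 does not plan SVR4 by genotype, so 0.5 point per subject in 200 is the relevant unit.
- **That the latest-value rule is in error because confirmed failure or later non-study therapy does not override it.** Section 6.3.3 removes post-treatment failures from the study. Section 6.2.4.2 calls for the Early Termination visit "except when the reason for discontinuation is confirmed virologic failure". On-treatment failure in the cited non-cirrhotic arms was (1 + 0 + 1)/(322 + 173 + 100) = 2/595 in genotype 1a with ribavirin, and 0/304 (509 − 205) in genotype 1b without it. A misleading value would also need new therapy and a captured later sample. That is a possible safeguard, not a demonstrated error.

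**Conclusion.** The point holds as a minor error in the floor of the SVR4 window. As written, the rule can report end-of-treatment suppression as response 4 weeks after completion, and nothing else in the documents prevents it. It does so only when no later sample through day 56 exists and the early sample is suppressed. Section 8 states no HCV RNA threshold for response, so suppressed here means whatever threshold is applied.

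The effect is 0.5 point per affected subject in 200, and at most about 0.6 point at the Table 2 adverse-event discontinuation rates. That ceiling assumes 100 subjects per arm, a modified intent-to-treat population close to 200, and rates like those in the cited trials. Leaving for other reasons would add to it by an amount the documents do not give. SVR4 is secondary and descriptive, with no formal comparison planned, so no main conclusion of the study depends on it.

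**What to change.** In Section 8 and the Protocol Summary:

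1. Open the SVR4 window at post-treatment day 23 (28 − 5, the lower limit of the PT Week 4 visit) and keep day 56 as the upper limit.
2. State that EOT and Early Termination samples before day 23 do not define SVR4.
3. Keep modified intent-to-treat subjects without a qualifying SVR4 value in the denominator. Count them as responders if their SVR12-window value shows response, so that SVR4 and SVR12 do not contradict each other, and otherwise as non-responders.

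Optionally, add a sentence that values obtained after the start of non-study anti-HCV therapy do not count as response.

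The cost is a wording change, with no new samples or visits. SVR4 may be slightly lower, and an occasional slightly early PT Week 4 sample, such as one on day 22, is not used.

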## **8.1 Demographics**

Demographics and baseline characteristics will be summarized for all subjects in the intent to treat population. Demographics include age, weight, height, and body mass index, and the frequency of gender, race, and ethnicity.

Baseline characteristics will include:

- HCV genotype 1 subtype (1a, 1b); interferon treatment history (treatment-naïve [interferon-eligible, interferon-ineligible] or interferon-based treatment experienced [null responder, partial responder, relapse, prior relapse/breakthrough, prior nonresponder, interferon intolerant and interferon experienced-other]);
- Baseline HCV RNA levels [(continuous)  $\leq 800,000$  IU/ or  $> 800,000$  IU/mL], baseline.

Summary statistics (number, mean, median, standard deviation and range) will be generated for continuous variables for example, age, and body mass index. The number and percentage of subjects will be presented for categorical variables for example, gender, and race.

## **8.2 Safety Outcome Measures**

The following safety evaluations will be analyzed during the study: AEs monitoring, and laboratory test assessments. Potential AEs that will be captured include those most commonly reported in the registration trials including headache, fatigue, nausea, pruritus, insomnia, diarrhea, asthenia, rash, cough, irritability, anemia and dyspnea.

All subjects who receive at least one dose of study drug will be included in the safety analyses.

## **8.3 Efficacy Analysis**

The primary efficacy analysis on clinical outcomes will be performed on all subjects in the intent to treat population. All other efficacy analyses will be performed on the modified intent to treat population

### **8.3.1 Primary Efficacy Endpoint**

The primary efficacy endpoint is to assess SVR12 in two subgroups of HCV (genotype 1a or 1b). The simple percentage of subjects achieving SVR12 will be calculated and a two-sided 95% confidence interval of the percentage will be computed based on Wilson's score method. We cannot know a priori how the 200 patients will be split into the two subgroups, but we expect each group to have approximately 100 patients (presumably between 80 and 120). Assuming a subgroup size of 100 each, the lower bound of the 95% confidence interval will

be within 7 percentage points of the observed SVR12 rate. Once the groups are fixed, the actual lower bound of the 95% confidence interval can be computed.

The observed SVR12 rate and confidence interval will be discussed in the context of results from randomized clinical trials, such as the SAPPHIRE-I/II trials and PEARL-II/III/IV trials described in the Background section. While formal statistical inference comparing results of this study to those of the randomized clinical trials will not be conducted, the point estimates and confidence intervals will be compared to assess the degree to which results from the real world setting are similar to or different from those in the randomized clinical trial setting. Results by prior treatment experience and response may be summarized if appropriate, based on the number of subjects enrolled in each subgroup. No subgroup sample size targets have been established.

### **8.3.2 Secondary Efficacy Endpoint**

The secondary efficacy endpoints are:

- To assess SVR4. The simple percentage of subjects achieving SVR4 will be calculated and a two-sided 95% confidence interval of the percentage will be computed based on Wilson's score method.
- Patient adherence with the VIEKIRA PAK regimen will be evaluated by review of study drug returned for drug reconciliation and/or compilation of patient reported compliance information.

## **9 ASSESSMENT OF SAFETY**

### **9.1 Safety Parameter and Definitions**

#### **9.1.1 Adverse Event (AE)**

An adverse event (AE) is any undesirable experience associated with the use of a medical product in a subject and includes the following:

- AE not previously observed in the subject during the protocol-specified AE reporting period, limited to signs or symptoms associated with Genotype 1 Chronic Hepatitis C and effects of study drug
- Complications that occur as a result of protocol-mandated activities
- AEs that occur prior to study treatment assignment that are related to a protocol-mandated activity
- Pre-existing medical conditions determined by investigator to have worsened in frequency or severity during the protocol-specified AE reporting period

#### **9.1.2 Serious Adverse Event (SAE)**

A Serious Adverse Event (SAE) is any adverse event that is any of the following:

- Fatal

- Life-threatening
- Requires initial or prolonged hospitalization
- Disability or permanent damage
- A congenital anomaly/birth defect in a neonate/infant that is suspect to exposure to a medical product prior to conception or during pregnancy
- A significant medical event determined by the investigator that may jeopardize the subject or may require medical or surgical intervention to prevent one of the outcomes listed above

### **9.1.3 Clinical Laboratory Abnormalities and Other Abnormal Assessments**

Laboratory abnormalities without clinical significance are not recorded as AEs or SAEs. However, in the event that the abnormalities require medical or surgical intervention, or lead to interruption, modification or discontinuation of either of the investigational drug, they must be recorded as an AE, and if applicable as an SAE. When reporting the AE, the event should be based on the syndrome or diagnosis, and not the lab result.

## **9.2 Methods and Timing for Capturing Safety Parameters**

The investigator is responsible for ensuring that all potential AEs (defined in [Section 9.1.1](#)) or SAEs (defined in [Section 9.1.2](#)) that occurred after subject provides written informed consent, but prior to initiation of study medication that are caused by protocol-mandated interventions will be collected and reported.

After initiation of study treatment, all AE and SAE probably related or possibly related to the study treatment or study-related procedures will be collected and reported until the end of study visit, or Early Termination.

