**Table 2: Overview of Treatment-Emergent Adverse Events (AE)**

	Placebo-Controlled		Regimen-Controlled		Cirrhotics	
	12-Week 3-DAA + RBV	12-Week PBO	12-Week 3-DAA + RBV	12-Week 3- DAA	12-Week 3-DAA + RBV	24-Week 3-DAA + RBV
Events, %	N = 770	N = 255	N = 401	N = 509	N = 208	N = 172
Subjects ≥ 1 AE	89.0	76.9	82.8	75.0	91.8	90.7
Severe AE	3.5	0.4	1.0	1.2	6.7	7.6
Grade 3 or 4 AE	3.9	0.8	3.0	2.0	7.7	8.1
Serious AE	2.1	0.4	2.2	1.4	6.3	4.7
AE leading to discontinuation	0.8	0.4	0.5	0.4	1.9	2.3
Deaths	0.1 a	0	0	0	0	0

DDA = Direct-Acting Antiviral; PBO: Placebo; aLung Cancer

The most common adverse events regardless of causality are listed in Table 3. Adverse events that occurred at ≥ 5% incidence in the 3-DAA and RBV regimen versus the placebo were considered to be adverse drug reactions related to the study treatment. These include fatigue, nausea, pruritus, insomnia, asthenia, and anemia. The frequency of these events was generally lower in the arm treated without ribavirin. In general, rates of adverse events were similar in patients with cirrhosis versus those without.

**Table 3: Treatment-Emergent Adverse Events with ≥ 10% Frequency in at Least One Arm of the Analysis and Rates of Key Post-Baseline Lab Abnormalities**

	Placebo-Controlled		Regimen-Controlled		Cirrhotics	
	12-Week 3-DAA + RBV	12-Week PBO	12-Week 3-DAA + RBV	12-Week 3- DAA	12-Week 3-DAA + RBV	24-Week 3-DAA + RBV
Treatment-emergent Adverse Events, %	N = 770	N = 255	N = 401	N = 509	N = 208	N = 172
Headache	34.3	29.8	24.4	25.1	27.9	30.8
Fatigue	34.2	26.3	29.9	26.5	32.7	46.5

	Placebo-Controlled		Regimen-Controlled		Cirrhotics	
	12-Week 3-DAA + RBV	12-Week PBO	12-Week 3-DAA + RBV	12-Week 3- DAA	12-Week 3-DAA + RBV	24-Week 3-DAA + RBV
Nausea	22.3	14.9	15.7	8.4	17.8	20.3
Pruritus	15.7	4.3	12.0	6.1	18.3	19.2
Insomnia	14.0	7.5	12.2	5.1	15.4	18.0
Diarrhea	13.5	9.0	8.7	11.4	14.4	16.9
Asthenia	13.5	6.7	9.0	3.9	13.9	12.8
Rash	10.0	5.9	6.2	3.7	11.1	14.5
Cough	8.7	5.1	6.7	4.7	11.5	11.0
Irritability	5.3	4.7	3.2	3.1	7.2	12.2
Anemia	5.3	0	7.5	0.2	7.7	10.5
Dyspnea	9.7	5.5	4.7	2.2	5.8	12.2
Laboratory Events, %	N = 765	N = 254	N = 401	N = 509	N = 208	N = 172
Hemoglobin						
< 10 g/dL (Gr 2)	5.5	0	6.2	0	7.2	11.0
< 8.0 g/dL (Gr 3)	0.1	0	0.5	0	1.4	0.6
ALT						
> 5 × ULN (Gr 3)	1.2	3.9	0.7	0.2	2.9	0
Bilirubin						
> 3 × ULN (Gr 3)	2.6	0	5.7	0.4	13.5	5.2

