### **1.6 Hypothesis**

Since the new treatment regimens do not cause the adverse events associated with the prior therapy, our hypothesis is that treatment with the VIEKIRA PAK (ombitasvir, paritaprevir/r, dasabuvir) with or without ribavirin will result in excellent outcomes in the real world setting and that the outcomes will be similar to those seen in the registration trials.

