### **9.2.1 Timing of Adverse Event (AE) Reporting**

All AEs occurring after the initiation of study treatment that are considered expected, and possibly or definitely related to the study (e.g. treatment) must be documented, and subsequently reported to the Sponsor-Investigator or designee at the end of the subject's participation in the study.

All AEs that are considered unanticipated, and possibly or definitely related to the study (e.g. treatment) must be reported to the Sponsor-Investigator or designee within 72 hours.

All unanticipated SAEs considered possibly or definitely related to the study (e.g. treatment) must be reported to the Sponsor-Investigator or designee within 24 hours of discovery.

Any AEs identified as occurring prior to the study treatment will be considered as part of the subject's medical history.

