### **9.2.2 Assessment of Serious, Severity, Causality and Unexpectedness**

Investigators are required to assess all AEs occurring after the initiation of study treatment for seriousness, severity, and causality as defined below.

Serious refers to events that pose a threat to a subject's life or vital functions and is based on subject or event outcome or action criteria. An AE that does not meet any criteria for serious, as defined in [Section 9.1.2](#) should be regarded as "non-serious" AE.

Severity refers to intensity of an AE as "mild," "moderate," or "severe":

- *Mild*: Symptom(s) that do not interfere with subject's usual social and functional activities
- *Moderate*: Symptom(s) that interfere to some extent with subject's usual social and functional activities
- *Severe*: Symptom(s) that interfere significantly with subject's usual social and functional activities

Causality refers to a reasonable possibility that the AE is related to the study medication or study-related procedure. If AE is not related to study medication or study-related procedure, investigators will assess the most likely cause of AE.

Unexpected refers to whether or not the AE is described as a risk in the package insert or investigator's brochure for the study drug(s), the protocol or in the informed consent form.

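### On-treatment adverse events are collected only if judged related, while other sections carry no such filter and the safety terms come from an all-causality table, so AE incidence is biased downward by an unknown amount

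*Combined protocol and SAP*

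**What the plan says.** Three places restrict which events enter the data.

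- Section 9.2: "After initiation of study treatment, all AE and SAE probably related or possibly related to the study treatment or study-related procedures will be collected". The rule covers serious as well as non-serious events.
- Section 9.2.1 (Timing of Adverse Event Reporting) makes documentation of expected events depend on relatedness; the sentence that sets this duty begins: "All AEs occurring after the initiation of study treatment that are considered expected, and possibly or definitely related to the study (e.g. treatment) must be". Its rules for unanticipated AEs and SAEs carry the same condition.
- Section 9.1.1 defines newly observed AEs as "limited to signs or symptoms associated with Genotype 1 Chronic Hepatitis C and effects of study drug".

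Two places carry no such filter.

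- Section 6.1.10 has clinical outcome events through post-treatment week 12 entered in the case report form as AEs or SAEs, and then points to Section 9.
- Section 9.2.2: "Investigators are required to assess all AEs occurring after the initiation of study treatment for seriousness, severity, and causality". For an unrelated event the investigator also assesses its most likely cause.

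The analysis section, 8.2, says: "Potential AEs that will be captured include those most commonly reported in the registration trials", and names "headache, fatigue, nausea, pruritus, insomnia, diarrhea, asthenia, rash, cough, irritability, anemia and dyspnea". Section 1.4 introduces the matching registration data: "The most common adverse events regardless of causality are listed in Table 3".

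**The concern.** The safety terms are taken from an all-causality table, but the rule that fills them admits only events an unblinded investigator attributes to treatment or procedures. The sections also conflict. Section 9.1.1 admits symptoms of hepatitis C as AEs, and 9.2 then drops them unless they are attributed to treatment. A site following 6.1.10 could record events that a site following 9.2 would leave out.

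Two things are at stake. First, incidence in this study would not mean what incidence means in Tables 2 and 3, and nothing in 8.2 says so. The hypothesis in 1.6 predicts that "the outcomes will be similar to those seen in the registration trials", so readers may well set the two side by side. Second, an event judged unrelated and never entered may not be recoverable at analysis, so a later change of attribution could not be examined.

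**Working it through.** **1. Match of terms.** The 12 terms in 8.2 and the 12 AE rows of Table 3 agree 12 for 12, in the same order.

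**2. The plan's own figure.** Section 1.4 calls an event a drug reaction if its incidence on 3-DAA + RBV exceeds placebo by at least 5 points, and names six. Differences from Table 3 (placebo-controlled columns, points):

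- At least 5: pruritus 15.7 − 4.3 = 11.4; fatigue 34.2 − 26.3 = 7.9; nausea 22.3 − 14.9 = 7.4; asthenia 13.5 − 6.7 = 6.8; insomnia 14.0 − 7.5 = 6.5; anemia 5.3 − 0 = 5.3.
- Below 5: headache 4.5; diarrhea 4.5; dyspnea 4.2; rash 4.1; cough 3.6; irritability 0.6.

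This reproduces the six named reactions. The other six terms in 8.2 fall outside that label, so there is room for an investigator to call them unrelated.

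**3. Direction.** Let r be the all-causality incidence and f the share of subjects with the event whose event is judged related. The collected incidence is f × r, which is at most r. Equality needs f = 1.

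**4. Size, by assumption.** The documents give no value for f, so it is varied. Inputs: r = 34.2% for fatigue (Table 3, 12-week 3-DAA + RBV, placebo-controlled column, N = 770), and n = 100, the subgroup size expected in 8.3.1. The plan sets no interval for AEs; the Wilson 95% interval it uses for SVR12 is borrowed here.

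Upper limit: U(x) = [p + z²/2n + z√(p(1−p)/n + z²/4n²)] / (1 + z²/n), with p = x/n and z = 1.96.

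U(24) = 33.2% and U(25) = 34.3%, so the whole interval lies below 34.2% when x ≤ 24. The chance is P(X ≤ 24), with X binomial (100, f × 0.342):

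| f | f × 34.2% | Chance that the whole interval is below 34.2% |
|---|---|---|
| 1.0 | 34.2% | 1.8% |
| 0.9 | 30.8% | 8.5% |
| 0.75 | 25.7% | 40% |
| 0.5 | 17.1% | 97% |

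At the ends of the plan's range for subgroup size and f = 0.75, the chance is 40% at n = 80 (x ≤ 19) and 48% at n = 120 (x ≤ 30). For a rare term such as irritability (5.3%), it stays under 7% at n = 100 even with f = 0.5.

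**5. Scale against Table 3 itself.** Table 3 has two columns for 12 weeks of 3-DAA + RBV outside the cirrhosis study:

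| Event | Placebo-controlled | Same × 0.75 | Regimen-controlled |
|---|---|---|---|
| Headache | 34.3% | 25.7% | 24.4% |
| Fatigue | 34.2% | 25.7% | 29.9% |
| Nausea | 22.3% | 16.7% | 15.7% |

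At f = 0.75 the loss is 8.6, 8.6 and 5.6 points. The two columns differ by 9.9, 4.3 and 6.6 points. The effect is of similar size to the spread between registration columns, and for headache and nausea the filtered rate still sits above the lower column.

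**The case against.** The strongest reply is that the plan never compares AE rates with the registration trials. Section 8.3.1 sets only SVR12 beside them, the objectives are SVR12, SVR4 and adherence, and 8.2 cites neither Table 2 nor Table 3. In 1.6, adverse events appear as a contrast with earlier therapy. This stands: there is no prespecified AE comparison to be biased. It does not remove the conflict between sections or the absence of any label on the basis of the counts.

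A second reply is that f may be close to 1. The filter admits events that are only possibly related, and 4.6.1 names fatigue, nausea, pruritus, insomnia and asthenia among the common reactions with ribavirin. This also stands; at f = 0.9 the single-symptom effect is small. A reader might infer a large gap from placebo incidence, which sums to 119.7 of 186.5 points (64%) over the 12 terms. That inference is not supported. Placebo incidence shows that background symptoms are common, but not how an investigator attributes an event in a subject known to be on treatment.

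A third reply is that 6.1.10 and 9.2.2 already cover all events. In part they do, so it is not established that unrelated events are lost. But 6.1.10 defers to Section 9, 9.2 is the specific collection rule there, and 9.2.2 asks for assessment without saying that unrelated events are entered.

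**Conclusion.** The inconsistency is real, and so is the downward direction wherever 9.2 is followed and any event is judged unrelated. The size is unknown. The figures for fatigue (8.5%, 40% or 97%, against 1.8%) rest on an assumed related share, 100 subjects, an unchanged true rate and an interval the plan does not specify for AEs.

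A reader might go further and infer that AE rates will fall below Tables 2 and 3 by construction, so that the regimen will look better tolerated than in registration. The documents do not support that. Only related ≤ all-causality holds by construction, and filtered rates can still exceed one of Table 3's own columns. Nor is 34.2% a genotype 1a benchmark: the placebo-controlled trials were 32.3% and 41.4% genotype 1b (Section 1.1).

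The primary and secondary efficacy endpoints are untouched. The point is worth correcting because it governs what the safety tables mean and the correction is cheap.

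**What to change.** Reconcile 6.1.10, 9.1.1, 9.2, 9.2.1 and 9.2.2 so that every treatment-emergent AE, or at minimum the 12 terms in 8.2, is recorded whatever its cause, with the 9.2.2 causality assessment kept as a separate field. Section 9.1.1 must be included, because its narrowed definition would otherwise keep any-AE incidence off the basis of Table 2. Use one relatedness scale: 9.2 speaks of probable and possible, 9.2.1 of possible and definite. In 8.2, specify two tables, one for all-causality and one for related AEs.

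If related-only collection is kept, title the tables as treatment-related AEs and state in 8.2 that they are not comparable with Tables 2 and 3.

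The cost is protocol wording, one case report form field and modest extra data entry. Appendix A already schedules AE review at every visit from Day 1 to post-treatment week 12, so no visit or procedure is added. The AE rates will look less favourable.
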